### **Intent to Treat Analysis**

Differences in change in outcomes will assessed using multi-level mixed models. Intra-class correlation coefficients will be obtained at the patient, clinic, and CHC organization levels for each outcome showed that much organization-level variance could be attributed to the clinic level. Thus, clustering was accounted for by random effects for clinic and patient, and a fixed effect for organization. Analyses will adjust for fixed effects: distribution of eligible patients by age, race / ethnicity, gender, rural / urban status, and federal poverty level (FPL) at index visit; number of ambulatory visits during the follow-up period; and time from index to last visit. These variables were selected *a priori* and will be confirmed by descriptive analyses, to determine whether there are significant differences between baseline intervention and control organization and patient characteristics. After checking distributions, negative binomial mixed-models or poisson mixed-model will be used for reversible risk analyses, and linear-mixed models for all other outcomes.

Patients diagnosed with diabetes during the follow-up period will be excluded from reversible risk analyses because diabetes might be diagnosed more often with CDSS use. Presence of diabetes raises reversible risk estimations even if CVD risk factor control was addressed; this exclusion will remove the possibility of confounding based on likelihood on new diabetes diagnosis.

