## 4. Study Design

CV WIZARD is a clinical decision support (CDS) tool that provides point-of-care cardiovascular disease (CVD) care recommendations to the primary care team and the patient. CV Wizard identifies a patient's uncontrolled CVD risk factors, prioritizes those factors based on potential CVD risk reduction for that patient, and generates specific guideline-based treatment recommendations for each uncontrolled risk factor.

We will recruit at least 60 safety net community health centers (CHCs) and randomize them to implement CV Wizard in study year 2 (Arm 1), or 18 months later (Arm 2). Prior to full implementation of the CV Wizard in Arm 1, two CHC organizations will be engaged to pilottest CV Wizard. The pilot sites will test the accuracy and usability of the tool in clinic workflows.

We will compare outcomes from Arm 1 (immediate implementation) and Arm 2 (delayed implementation), which will enable us to measure the intervention's impact on CVD risk factor control in CHCs. Arm 1 CHCs will receive implementation support to address any barriers to adoption/sustained use of the CDS tool that are identified through study activities. We will apply these learnings to improve adoption rates in Arm 2.

Through this design, we will (1) assess whether this CDS tool is effective in CHCs, (2) identify and address barriers to its effectiveness and adoption, and (3) fine-tune strategies to support implementation of CDS systems in CHCs. To meet these aims, we will conduct mixed methods analyses (described below). Our assessment includes interviews with CHC staff, providers, and patients to determine if use of CV WIZARD increases patient engagement in CVD treatment choices.

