## Clinic Identification, Recruitment & Assignment

Clinics will be included in the recruitment pool for this study if they (1) provide primary care to adults with high CVD risk annually, and (2) have been using OCHIN's EHR for at least 18 months. Once all clinics have been recruited as outlined in Section 5.e., they will be assigned to either arm 1 or arm 2. Clinics were grouped based on the baseline number of encounters each service area had, percent of patients with hypertension, and percent of patients who use tobacco. Five randomly generated groupings were created and the grouping that created the most even distribution across both Arms was then selected to assign service areas and the clinics within each service area to an Arm.

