## 7. Data Analysis

### a. Analysis Plan

#### Overview

In this service area pragmatic clinical trial, we will implement CV Wizard via a staggered process. We will compare patients' CVD outcomes in the Arm 1 vs. Arm 2 CHCs, in months 18-35 (Aim 1); assess whether the revised implementation support materials expedite CDS adoption (Aim 2); and use mixed methods to identify multi-level barriers/facilitators to adoption of the CDS tool (Aim 3).

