We will also examine overall rates of each of the impact outcomes (BMI in normal range, controlled blood pressure, controlled LDL, controlled HbA1c, and non-smoking status) pre/post tool use to assess any changes in patterns for patients in Arm 1 for whom the tool was used compared to those in Arm 1 for whom the tool was not used as well as to Arm 2 patients. The date the tool was first used for each patient will be assigned as the start of the post-period.

Extent of adoption of a CDS tool like CV Wizard directly impacts its population-level impact. To differentiate between the tool's population level impact versus impact when used, we will conduct intent to treat (ITT) analyses to compare all targeted patients at intervention versus control clinics. We will also conduct effect of treatment on the treated (ETOT; also called per protocol) analyses limited to intervention CHC patients for whom the CV Wizard tool was used (results viewed / printed out) at the index visit, compared to intervention clinic patients for whom it was not used, and separately, to control clinic patients. The ITT analyses test the hypotheses that targeted patients in intervention clinics will have significantly lower CVD risk scores and higher rates of CVD risk factor control, at visits in the year post-index visit period, compared to similar patients in control clinics. The ETOT analyses test the hypotheses that targeted patients in intervention clinics for whom the CV Wizard CDS tool results are viewed and / or printed will have significantly lower CVD risk scores and higher rates of CVD risk factor control, at visits in the year post-index visit period, compared to similar patients in control clinics, and compared to patients in intervention clinics for whom the tool alerted but was ignored at the index visit.

Analyses will be stratified by first-time and repeat patients to see if there is a difference in tool use as well as examine whether the time between visits effects tool use among repeat patients.

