#### **Effect of Treatment on the Treated Analysis**

Per-protocol analyses require adjusting for loss to follow-up and off-protocol therapies or treatments, but if group differences vary too greatly, model misspecification can yield biased estimates. Propensity score methods are an alternative. We will match intervention organization patients in three categories of tool use (never used during follow-up, used once, used more than once) to control organization patients. Counts of tool use will include use at index visit or subsequent study period visits, excluding the last visit. Matching variables will include age, FPL, outcome of interest at baseline, race / ethnicity, sex, count of ambulatory care visits post-index

visit, time from index visit to last study period visit, and clinic rural / urban status. Propensity scores will be estimated using nearest-neighbor matching with replacement.

As analyses in other settings indicated CV Wizard's potential for greater impact among patients with higher baseline risk, analyses of change in reversible risk will be stratified by baseline risk <10% or ≥10%. The assumption being that patients with lower baseline risk are less likely to improve. Additionally, we will run analyses by quartile of baseline reversible risk among patients for whom the tool was ever used during follow-up, matched to controls as described above. Analyses of change in reversible risk will include all patients meeting study inclusion / exclusion criteria; for other outcomes, analyses were restricted to patients with uncontrolled baseline risk. Linear mixed models will be used for all outcomes and checked for normality of residuals.

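### The ITT model fixes organization, which appears to be nested in arm: an arm main effect is then not estimable, and the arm-by-time term that is estimable is never specified

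*Combined protocol and SAP*

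**What the plan says.** Section 7.a, Intent to Treat Analysis, gives the clustering structure: "Thus, clustering was accounted for by random effects for clinic and patient, and a fixed effect for organization". It describes the target as between-arm differences in change. It prescribes count mixed models for reversible risk and linear mixed models for the other outcomes. It writes no model equation and names neither an arm term nor an arm-by-time term.

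On assignment, section 6.a (Clinic Identification, Recruitment & Assignment) says the chosen grouping was used to "assign service areas and the clinics within each service area to an Arm". The Overview in 7.a agrees: "In this service area pragmatic clinical trial, we will implement CV Wizard via a staggered process". The analysis text then classes organizations by arm. The ITT section refers to "whether there are significant differences between baseline intervention and control organization and patient characteristics", and the treatment-on-the-treated section says "We will match intervention organization patients in three categories of tool use" and matches them to control-organization patients. Elsewhere the randomized unit is the clinic. Section 4 says "We will recruit at least 60 safety net community health centers (CHCs) and randomize them to implement CV Wizard", and the Specific Aims and section 5.a read the same way.

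The effect being tested is worded in more than one way. Section 7.a, Quantitative Data, puts the ITT hypotheses as lower risk and better control "at visits in the year post-index visit period, compared to similar patients in control clinics". Secondary Outcome Measures in 6.a defines the control outcomes by the last value and the ASCVD score as a change to the last visit. Only Statistical Power mentions a group-by-time interaction.

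**The concern.** A fixed effect for a unit nested in the treatment arm uses up the treatment contrast. If every organization is wholly in one arm, the organization indicators already determine arm, and no information about arm as a main effect remains. This affects the point estimate itself and not only its standard error. Adding a random service-area term while keeping the fixed organization effect would not cure it.

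The primary effectiveness comparison of Aim 1 is at stake. An analyst who takes the hypotheses in Quantitative Data and fits them with the structure in the ITT section has no valid arm estimate. An analyst who fits arm by time has an estimate, but its standard error ignores variation in change at what appears to be the level of assignment. The plan does not say which model is meant.

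**Working it through.** The plan reports no Aim 1 power value, SD or ICC, so there is no figure to reproduce. The question is identifiability.

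**Inputs.** From Statistical Power: 60 clinics with more than 35 patients each; 36 per clinic is used here. From the ITT section: fixed organization, random clinic and patient. Assumed: 6, 12, 20 or 30 organizations (G), because the documents give no number; organizations nested in arm; five patient covariates.

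**Step 1: arm as a main effect.** The G organization columns sum to the intercept, so with five covariates the rank is G + 5. Arm is the sum of the Arm 1 organization columns and adds nothing. The same holds if the response is a follow-up value, a last value or a change score. Random effects and a log link do not alter the fixed-effect column space.

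**Step 2: index and follow-up values in one model.** Adding a time column gives rank G + 6. The arm main effect is still aliased. The arm-by-time column varies within organization, so the rank rises to G + 7. If fixed organization-by-time effects are added, the base rank is 2G + 5 and arm by time is aliased again.

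| G | Follow-up or change model, adding arm | Index + follow-up, adding arm | Index + follow-up, adding arm by time | With fixed organization-by-time, adding arm by time |
|---|---|---|---|---|
| 6 | 11 to 11 | 12 to 12 | 12 to 13 | 17 to 17 |
| 12 | 17 to 17 | 18 to 18 | 18 to 19 | 29 to 29 |
| 20 | 25 to 25 | 26 to 26 | 26 to 27 | 45 to 45 |
| 30 | 35 to 35 | 36 to 36 | 36 to 37 | 65 to 65 |

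If one organization is split across arms, arm becomes estimable in the follow-up model (17 to 18 with G = 12), but only from that organization.

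**Step 3: what software would print in the aliased model.** This is illustrative only and applies only if an arm main-effect model is fitted. One simulated data set had 12 organizations, a true effect of -0.20, assumed organization and clinic SDs of 0.1 and a patient SD of 1. The arm coefficient ran from -0.62 to +0.31 over six choices of dropped organization indicators. Each value equalled the difference between the two reference organizations.

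**Step 4: an averaged organization-within-arm contrast.** Some software returns this instead. It treats the organizations as fixed and leaves their variation out of the error. With an assumed clinic ICC of 0.01 and organization ICCs of 0.005, 0.01 and 0.02, simulated type I error at nominal 5% was 12.2%, 20.2% and 30.1% with 12 organizations, and 9.5%, 14.4% and 22.2% with 20. At organization ICC 0 it was 5.5% and 4.6%. A comparison at organization level stayed between 4.6% and 5.7% throughout.

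**Step 5: the arm-by-time model as specified.** Fixed organization and random clinic and patient intercepts absorb differences in level. None absorbs differences in change between organizations. If a share ρ of the variance of change lies between organizations, and m is the number of patients per organization, the variance of the arm-by-time estimate is understated by about 1 + (m - 1)ρ, with m = 60 × 36 / G. Clinic-level variation in change is set to zero here. Under the same assumed range of ρ:

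- G = 12, m = 180: 1 + 179 × 0.005 = 1.90 up to 1 + 179 × 0.02 = 4.58
- G = 20, m = 108: 1 + 107 × 0.005 = 1.54 up to 1 + 107 × 0.02 = 3.14
- G = 30, m = 72: 1 + 71 × 0.005 = 1.36 up to 1 + 71 × 0.02 = 2.42

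Taking square roots, the standard error would be too small by a factor of about 1.2 (√1.36) to 2.1 (√4.58). This is a linear-model approximation and depends on ρ, which the documents do not give.

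**The case against.** The strongest reply is that the plan probably intends the arm-by-time model, in which the fixed organization effect does no harm to identifiability. The ITT section speaks of differences in change. A patient random effect implies several rows per patient, since with one row a linear model could not separate it from the residual. A signed change score cannot be the response in a count model. Quantitative Data calculates status at the index visit and at each follow-up encounter. The power text varies a group-by-time effect. Under that reading the aliased arm main effect is harmless, because it is not the treatment effect.

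Most of this stands. A reader might infer that the ITT effect cannot be estimated at all, that software will drop a column, or that the primary model will have to be changed after the data are seen. The documents do not support those inferences. The clustering sentence is also in the past tense, which suggests that the structure was chosen after ICCs had been examined.

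The reply does not close the matter. A follow-up-only model using every post-index encounter could also carry a patient random effect, and that is how the hypotheses are worded. For reversible risk, the count model leaves either follow-up values, where arm is aliased, or arm by time, which the analysis section never writes. The arm-by-time reading also still omits organization-level variation in change. The section's remark that much organization variance could be attributed to clinics gives no value and does not address change.

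A second reply is that nesting is inferred. That is correct. No section equates service area with organization, and several sections describe clinic randomization. If some organizations straddle arms, arm is estimable, but only from those organizations, a comparison the plan nowhere describes.

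**Conclusion.** The point holds in a conditional form. If organizations are nested in arm, the arm main effect is perfectly collinear with the fixed organization effects. The follow-up-value hypotheses, the last-value control outcomes and any change-score model then yield no arm estimate under the stated structure, whatever the number of organizations. An arm-by-time term in a model holding index and follow-up values is estimable; the power text implies it, the ITT section does not state it, and as specified its error excludes between-organization variation in change.

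The aliasing result rests only on nesting, which is supported by the assignment text and by the intervention and control organization labels but is not stated. The type I error and standard-error figures rest on assumed numbers of organizations and assumed ICCs. They show direction and plausible range and do not estimate this trial's error. The plan should be changed because the effect tested in the Aim 1 ITT analysis is not fixed by its text.

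**What to change.** 1. In Intent to Treat Analysis, write out the model and name the arm-by-time contrast as the ITT effect for every outcome modelled at index and follow-up.
2. Replace the fixed organization effect with a random effect at the level of assignment (service area or organization). Add a random organization-by-time effect wherever index and follow-up values are both modelled.
3. State that no follow-up-only, last-value or change-score model contains fixed organization effects.
4. Define service area and organization, say whether any organization has clinics in both arms, and reconcile section 6.a and the Overview in 7.a with the clinic-randomization wording in the Specific Aims, section 4 and section 5.a.

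Naming arm by time while keeping organization fixed would settle identifiability alone, but would leave the error term too small if organizations differ in change. The cost is wording only, with no new data, and a somewhat wider interval because organization differences in change enter the error. If those differences are negligible, the widening should be small.

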### **Specific Aims**

**Aim 1.** Conduct a clinic-randomized trial of the impact of an evidence-based point-of-care CDS system on (i) overall CVD risk scores, and (ii) control of individual CVD risk factors (blood pressure; HbA1c, lipid levels; smoking; body mass index), among high CVD risk adult CHC patients.

**Aim 2.** Develop and hone need-based implementation support protocols to help Arm 1 CHCs implement the CV Wizard CDS system into their standard workflows; assess whether use of the protocols developed for Arm 1 CHCs accelerates implementation and adoption of the CDS system in the Arm 2 CHCs. **Supplement Addendum:** Compare CVD risk management in high-risk patients at in-person vs. virtual care (VC) encounters, in the periods pre- and post-COVID's onset.

**Aim 3.** Conduct a mixed methods process evaluation, guided by the Technology Acceptance Model (TAM), to identify and address patient, provider, and delivery system barriers to uptake/impact of this CDS in CHCs. **Supplement Addendum:** In a subset of study clinics, explore how CV Wizard's individualized, prioritized CVD risk summary is used in VC to guide care decisions and engage patients in shared decision-making.

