### 5. Study Population

## a. Number of Subjects

NOTE: This study does not include any KP subjects.

### Study Aim 1

Clinics – We will randomize at least 60 CHCs from within the OCHIN collaborative to either immediate (Arm 1) or delayed (Arm 2) CV Wizard tool implementation. While CV Wizard will be used with patients in those clinics, they are not considered study subjects.

### Study Aim 2

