#### **Quantitative Data**

To be included in Aim 1 analyses a patient must have at least one visit in the 6 months after the Arm 1 implementation date at an Arm 1 or Arm 2 CHC and at least one additional visit at a study clinic in the 12-month post-index visit period. The first visit is referred to as the index visit. We will describe those who had inadequate follow-up data (did not have at least one additional visit in the post-index period). For each study subject, CVD risk score / risk factor management status will be calculated at index visit and each encounter during follow-up. While the tool can be run for patients of any age, we will restrict our analyses to patients 40-75 years of age.

We will test for between-group differences in baseline characteristics such as age, sex, race and ethnicity, insurance type, visit count, and health status using chi-square, t-test, and nonparametric Wilcoxon rank-sum tests as appropriate. We will also test for association between baseline characteristics and our outcomes of interest. We will examine the number of patients seen in each service area and clinic and each Arm and compare the characteristics of Arm 1 patients for whom the tool was used to those in Arm 1 for whom the tool was not used and to Arm 2 patients. Because the two arms were selected based on clinic size, percent of patients with a diagnosis for hypertension and the percent of patients that use tobacco, we anticipate there will be differences between the two groups resulting in the need to adjust for these differences. We will also examine characteristics at the service area and clinic-level in Arm 1 for whom the tool was used compared to Arm 1 service areas / clinics for whom the tool was not used and Arm 2 service areas / clinics.

Unadjusted trends in the monthly use and view rates for each of the study CHCs will be explored with use rates defined as: the number of encounters where CV Wizard was printed / number of targeted encounters with high-CVD risk patients per month and view rates defined as the number of encounters where CV Wizard was viewed / number of targeted encounters with high-CV risk patients per month.

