#### Statistical Power

To conservatively calculate power for our main outcome (CVD risk score) we estimated 60 clinics with >35 high-CVD risk patients, randomized to two arms; then, using means and standard deviations for this measure from previous studies, we varied effect size associated with the group x time interaction and intraclass correlation. We examined a 1.5%, 2%, 3% greater absolute reduction in risk score over time in intervention vs. control CHCs. Aggressive management can reduce 10-year CVD risk by an absolute 4-5% in high-risk patients in a short time. We do not expect so large an effect and have power to detect smaller effects. **Supplement Addendum (Aim 2b).** This is a 2x2 repeated measures design with two groups of subjects measured at two time points. The primary goal is to compare change across time in group 1 (inperson index encounters) to change across time in group 2 (VC index encounters). A conservative estimate (based on preliminary results from the parent study) of 6000 patients in group 1 and 6000 in group 2 achieve 100% power to detect a difference in mean changes in CVD risk score of 5.0, with a standard deviation of 9.1 at the first time point, a standard deviation of 9.1 at the second time point, and a correlation between measurement pairs of 0.200. The significance level (alpha) is 0.050 using a two-sided, two-sample t-test.

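### Service areas were assigned to arms, but the ITT model has no service-area term, so the standard error of the arm difference in change may be too small

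*Combined protocol and SAP*

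**What the plan says.** Two places make the service area the unit of assignment. Section 6.a (Clinic Identification, Recruitment & Assignment) describes five random groupings built on service-area characteristics, the most even of which was "selected to assign service areas and the clinics within each service area to an Arm". The Overview in section 7.a opens: "In this service area pragmatic clinical trial, we will implement CV Wizard via a staggered process". The Quantitative Data text treats area and clinic as separate levels: "We will examine the number of patients seen in each service area and clinic and each Arm".

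Other places name a different unit:
- Specific Aims, Aim 1: "Conduct a clinic-randomized trial of the impact of an evidence-based point-of-care CDS system"
- Section 4, Study Design: "We will recruit at least 60 safety net community health centers (CHCs) and randomize them to implement CV Wizard"
- Section 5.a, Number of Subjects: "We will randomize at least 60 CHCs from within the OCHIN collaborative"
- Section 5.d, OCHIN procedures: lists the randomization of clinics as a task
- Statistical Power: "we estimated 60 clinics with >35 high-CVD risk patients, randomized to two arms"

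The Intent to Treat Analysis targets differences in change and states that "clustering was accounted for by random effects for clinic and patient, and a fixed effect for organization". It justifies this by ICCs at patient, clinic and organization level, reporting that a good part of the organization-level variance sat at clinic level. It plans Poisson or negative binomial mixed models for reversible risk. No service-area ICC, number of areas, or mapping of areas to organizations is given.

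**The concern.** When whole service areas go to one arm, whatever makes the patients of one area improve together, other than the tool, adds to the error of the arm comparison. A model that treats the clinics of one area as independent leaves that shared part out. The confidence interval is then too narrow and the false-positive rate exceeds its nominal level. This model carries the primary Arm 1 vs Arm 2 comparison of reversible risk, so the main conclusion of the trial is exposed. The conflict over the randomized unit matters for the same reason: a reader who takes clinics as the unit would see nothing missing from the model.

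**Working it through.** The plan gives no power, SD or ICC for the main outcome, so it has no figure to reproduce. The check has two parts.

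**1. Does the organization fixed effect cover the service area?** Take the most favourable case: each organization is one service area, with 20 of them, each in one arm.
- Repeated measures: 20 organization intercepts + time + arm-by-time = 22 columns, rank 22. The arm difference in change can be estimated. The intercepts remove differences in level between areas. They do not put area-to-area variation in change into the error.
- One change value per patient: 20 organization effects + arm = 21 columns, rank 20. The arm effect cannot be separated from the organization effects.

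**2. How large could the understatement be?**

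Inputs from Statistical Power: 60 clinics and n = 35 patients per clinic (the plan says more than 35). Assumed: equal arms; A = 20 areas, so k = 60/20 = 3 clinics per area; ICC of change ρ = 0.01; share s of the cluster variance at area level; clinic random effects on change fitted.

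Variance of the arm difference, relative to independent patients:
- as a clinic-level model sees it: V_c = 1 + (n − 1)ρ = 1 + 34 × 0.01 = 1.34
- as it is: V_a = V_c + (k − 1)·n·s·ρ = 1.34 + 2 × 35 × 0.01 × s = 1.34 + 0.70s

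The true SE is √(V_a/V_c) times the model SE. Type I error is the two-sided tail of t with 58 df beyond 2.002/√(V_a/V_c).

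| s | V_a | SE ratio | cut-off | type I error |
|---|---|---|---|---|
| 0.2 | 1.48 | 1.051 | 1.905 | 6.2% |
| 0.5 | 1.69 | 1.123 | 1.782 | 8.0% |
| 1.0 | 2.04 | 1.234 | 1.622 | 11.0% |

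The same formula over the same shares gives 6–8% with 30 areas (k = 2) and 8–19% with 10 areas (k = 6). With k = 1, or with ρ = 0, V_a = V_c and the rate is 5%.

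Simulation checks:
- Linear, 3 clinics per area, ρ = 0.02, s = 0.5 (4,000 runs): clinic-level test 9.9%, area-level test 4.6%. The formula gives √(2.38/1.68) = 1.190 and 9.8%. With one clinic per area both tests give 5.2%; with no cluster variance in change, 5.1% and 5.2%.
- Poisson counts with an assumed mean of 8, 20 areas, ρ = 0.01, s = 0.2/0.5/1 (8,000 runs each): clinic-level test 6.4/8.2/12.0%, area-level test 5.2/4.7/5.3%.
- The same, choosing the best of five groupings and assuming that the balancing variables explain 25% of area variation in change: clinic-level test 5.7/7.8/10.0%.

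A negative binomial mixed model was not fitted, and the plan's covariates were not simulated.

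**A separate issue: random intercepts only.** If the clinic and patient effects act on level alone, no cluster variation in change is captured. Type I error is then 2(1 − Φ(1.96/√V_a)). With one clinic per area this is already 9.0% (1.96/√1.34 = 1.693); with 20 areas it is 10.7/13.2/17.0%.

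**The case against.** The best defence is the plan's own ICC rationale. If organization and service area coincide or nearly so, the finding that a good part of organization-level variance lies at clinic level argues for the lower area shares, where the illustrated rate is about 6%. That lowers the likely size but does not close the point: no service-area ICC is reported, the ICCs are not said to concern change, and a good part is not all. It is also fair that every input driving the size is assumed and that the fault disappears with one clinic per area. The assignment text, however, speaks of clinics in the plural within each area.

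Three stronger readings are tempting, and the documents do not support them.
- *The primary comparison cannot be computed.* That needs one change value per patient and every organization wholly in one arm. For reversible risk, a patient random effect and count models, which cannot take negative change values, point to repeated measures. The baseline-to-last-visit wording belongs to a secondary outcome.
- *Missing service areas push the error rate to 11–17%.* Those figures (10.7/13.2/17.0%) assume intercepts only and mix in a different defect, which gives 9% even with one clinic per area. The plan neither states nor excludes effects on change.
- *The power statement is wrong.* The section gives no power figure, and the smaller effects it mentions are those below 4–5 points. Nothing stated there is shown to be false.

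**Conclusion.** The point stands in conditional form. The randomized unit is stated inconsistently, and the primary model has no term for the unit that was assigned. For reversible risk as repeated measures, the arm-by-time contrast can be estimated, but its standard error is too small if areas hold several clinics and change varies between areas. With the assumed 20 areas and ICC of change of 0.01, type I error is about 6, 8 or 11% for area shares of 20, 50 or 100%. The documents allow no firmer size, and the true figure could be no inflation at all.

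Two cautions stand beside this. Intercept-only random effects would understate the error even with one clinic per area. And for any outcome analysed as one change value per patient, the arm effect cannot be estimated beside organization fixed effects if each organization lies in one arm. The labelling of organizations as intervention or control suggests that they do, without saying so.

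**What to change.** - Reconcile the Specific Aims, sections 4, 5.a, 5.d and 6.a, the Overview and Statistical Power on one randomized unit.
- State the number of service areas and how they map to organizations and clinics.
- In the Intent to Treat Analysis, say whether each outcome is modelled as repeated visits or as one change value, and name the arm contrast (arm-by-time, or arm).
- Add a random service-area effect on change: service-area-by-time for repeated visits, or a service-area effect in a change-score model. Keep the clinic effect, and the patient effect for repeated visits. Analysing service-area-level change is an alternative.
- Base the degrees of freedom on the number of service areas, with a small-sample method suited to the model.
- In any change-score model where each organization lies in one arm, replace the organization fixed effect with the random service-area effect. If organizations span arms, it may stay.
- Describe the power basis with service areas as clusters, giving the ICC of change, the SD and the resulting power or detectable difference.

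The cost is SAP wording and a re-run of the model and the power calculation, with no new data or patients. Intervals become wider and degrees of freedom fall. If areas are few, the area variance will be imprecise. If each area proves to hold one clinic, saying so and fitting clinic effects on change would settle the service-area part.
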